10.1.2 Solicited Adverse Events

The occurrence of selected indicators of safety will be measured/collected for 7 days after trial vaccine administration (including the day of administration) and will be recorded on the local and systemic AEs eCRF page as applicable and as listed in [Table 10.a](#).

Any solicited local or systemic AEs observed as continuing on Day 8 trial vaccine administration will be recorded as an AE on the AE eCRF for follow-up. For these persistent/prolonged solicited AEs the end date will be captured on the AE eCRF to permit a separate analysis from the unsolicited AEs (see Section [10.4.2](#)).

Table 10.a Solicited Local and Systemic AEs

Solicited local AEs:	Erythema Induration Swelling Pain
Systemic AEs:	Headache Fatigue Myalgia Arthralgia Vomiting Diarrhea Fever*

Body temperature will be collected and recorded. *Fever is defined as body temperature $\geq 38^{\circ}\text{C}$ (100.4°F) regardless of method used [25].

The severity of solicited safety parameters will be assessed as described in [Table 10.b](#).

Table 10.b **Solicited Safety Parameters**

Adverse Event	Severity Grade	Intensity
Pain at injection site	0	None
	1	Mild: No interference with daily activity
	2	Moderate: Interference with daily activity with or without treatment
	3	Severe: Prevents daily activity with or without treatment
Erythema at injection site ^(a)	0	<25 mm
	1	Mild: $\geq 25 - \leq 50$ mm
	2	Moderate: $>50 - \leq 100$ mm
	3	Severe: >100 mm
Induration at injection site ^(a)	0	<25 mm
	1	Mild: $\geq 25 - \leq 50$ mm
	2	Moderate: $>50 - \leq 100$ mm
	3	Severe: >100 mm
Swelling at injection site ^(a)	0	<25 mm
	1	Mild: $\geq 25 - \leq 50$ mm
	2	Moderate: $>50 - \leq 100$ mm
	3	Severe: >100 mm
Headache	0	None
	1	Mild: No interference with daily activity
	2	Moderate: Interference with daily activity with or without treatment
	3	Severe: Prevents daily activity with or without treatment
Fatigue	0	None
	1	Mild: No interference with daily activity
	2	Moderate: Interference with daily activity
	3	Severe: Prevents daily activity
Myalgia	0	None
	1	Mild: No interference with daily activity
	2	Moderate: Interference with daily activity
	3	Severe: Prevents daily activity
Arthralgia	0	None
	1	Mild: No interference with daily activity
	2	Moderate: Interference with daily activity
	3	Severe: Prevents daily activity
Vomiting	0	None
	1	Mild: No interference with activity or 1 – 2 episodes/24h
	2	Moderate: Some interference with activity or >2 episodes/24h

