10.4.2 Collection and Reporting of Solicited Adverse Events

The occurrence of selected indicators of safety will be collected in the diary card by the subject for 7 days after administration of the trial vaccine (including the day of administration, corresponding to Day 1 and will be recorded on the local and systemic AEs eCRF, as applicable. These will be summarized in the final CSR under the category solicited AEs to differentiate them from unsolicited AEs. Any solicited local (injection site) or systemic AE observed as continuing on Day 8 after the trial vaccine administration will be recorded as an AE on the AE eCRF for follow-up. For these persistent/prolonged solicited AEs, the end date will be captured on the AE eCRF to permit a separate analysis from the unsolicited AEs.

Any solicited AE that meets any of the following criteria must be entered as an AE on the AE eCRF page:

- Solicited local or systemic AEs that lead the subject to withdraw from the trial.
- Solicited local or systemic AEs that lead to the subject being withdrawn from the trial by the investigator.
- Solicited local and systemic AEs that otherwise meet the definition of an SAE (see Section 10.1.2).

10.4.3 Collection and Reporting of Adverse Events of Special Interest/Medically-Attended Adverse Events

AESIs and MAAEs will not be collected.

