#### **10.1.3 Solicited Adverse Events**

The solicited safety parameters for this study are the local adverse events (injection site reactions) of pain, erythema (redness), induration and swelling and the systemic adverse events of headache, fatigue, myalgia, arthralgia, vomiting, diarrhea and fever (defined as body temperature greater than or equal to 38°C regardless of methods used).

Solicited reactions will be assessed 30 minutes after administration of the trial vaccine, and then daily for 7 days (including the day of administration).

Body temperature measurements will be summarized in categories (including fever), without adjustment for the route of measurement. Summaries of the day of first onset of each event and the maximum number of continuous days subjects experienced each event will also be provided.

Any solicited local or systemic reactions observed as continuing beyond 7 days following the trial vaccine dose will be recorded as an unsolicited AE in the case report form (CRF).

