##### **10.1.3.1 Summaries**

The summaries for solicited AEs will be:

- The number and percentage of subjects with solicited local and systemic reactions during the first 7 days (including day of administration) after the trial vaccine dose by day and overall.
- The number and percentage of subjects with solicited local and systemic reactions during the first 7 days (including day of administration) after the trial vaccine dose by severity, day and overall.
- The number and percentage of subjects with solicited local and systemic reactions during the first 30 minutes after the trial vaccine dose.

- The number and percentage of subjects with solicited local and systemic reactions during the first 30 minutes after the trial vaccine dose by severity.
- Summary of the day of first onset of each solicited AE.
- Summary of the duration (days) of each solicited AE.

A horizontal stacked bar plot showing the percentage of participants with each solicited AE after the trial vaccine dose. This plot will break down the percentages by maximum severity, with the percentage of mild, moderate and severe events stacked for each solicited AE.

All solicited AEs will also be listed.

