#### **10.1.4 Unsolicited Adverse Events**

Unsolicited AEs will be collected up to 28 days after administration (including the day of administration) of the trial vaccine. Only unsolicited AEs recorded after the dose of trial vaccine will be summarized. All AEs will be listed with the timing relative to dose of trial vaccine.

Any unsolicited AEs will be summarized using the day of onset for the following 3 time intervals:

- 1) Day 1 to Day 28,
- 2) Day 1 to Day 7,
- 3) Day 8 to Day 28.

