##### **10.1.4.1 Summaries**

The summaries for unsolicited AEs will be:

- Overall Overview of the occurrence of all AEs.
- The number and percentage of subjects with any unsolicited AE during the first 28 days (including day of administration) after the trial vaccine dose.
- The number and percentage of subjects with any unsolicited AE during the first 28 days (including day of administration) after the trial vaccine dose by severity.
- The number and percentage of subjects with any unsolicited AE during the first 28 days (including day of administration) after the trial vaccine dose by relatedness to the trial vaccine.
- The number and percentage of subjects with any unsolicited AE during the first 28 days (including day of administration) after the trial vaccine dose by relatedness to the trial procedures.

Listings will be presented for all unsolicited AEs.

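### SAP 10.1.3 labels solicited reactions that outlast the 7-day window as unsolicited AEs, and nothing in SAP 10.1.4 keeps them out of the unsolicited tables, although the protocol treats them as persistent solicited AEs

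*SAP*

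**What the plan says.** **Protocol.** Sections 10.1.2 and 10.4.2 have solicited reactions recorded for 7 days, counting the vaccination day as Day 1. A reaction still present on Day 8 goes on the AE eCRF as an AE. Section 10.1.2 gives the purpose: "the end date will be captured on the AE eCRF to permit a separate analysis from the unsolicited AEs". Section 10.4.2 repeats this and names the class of event: "For these persistent/prolonged solicited AEs, the end date will be captured on the AE eCRF". On the 7-day diary events, 10.4.2 adds: "These will be summarized in the final CSR under the category solicited AEs to differentiate them from unsolicited AEs".

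Section 10.4.2 also sends to the AE eCRF any solicited AE that leads to withdrawal or is serious, whether or not it continues on Day 8.

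**SAP.** Section 10.1.3 says that a solicited local or systemic reaction "observed as continuing beyond 7 days following the trial vaccine dose will be recorded as an unsolicited AE in the case report form (CRF"). The solicited tables in 10.1.3.1 count subjects with "solicited local and systemic reactions during the first 7 days (including day of administration) after the trial vaccine dose by day and overall". For the unsolicited tables, 10.1.4 states one filter: "Only unsolicited AEs recorded after the dose of trial vaccine will be summarized". It then says: "Any unsolicited AEs will be summarized using the day of onset for the following 3 time intervals" (Day 1 to 28, Day 1 to 7, Day 8 to 28). Section 10.1.4.1 tabulates any unsolicited AE over 28 days, also by severity and by relatedness, for example "subjects with any unsolicited AE during the first 28 days (including day of administration) after the trial vaccine dose by relatedness to the trial vaccine". SAP 13 says only that the SAP is based on protocol version 3.0.

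**The concern.** Solicited AEs (up to 7 days) and unsolicited AEs (up to 28 days) are separate secondary endpoints in both documents. The protocol keeps a prolonged solicited reaction identifiable as solicited. The SAP relabels it as unsolicited, and no later SAP rule undoes the label. A programmer who follows the SAP would count one event under both endpoints.

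At stake is the accuracy of the reported unsolicited AE percentages. The effect can only be upward, and a reader of the tables could not tell how much of the unsolicited rate consists of reactions already shown as solicited. The safety objective is the only secondary objective, and its output is these counts.

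**Working it through.** There is no plan figure to reproduce: the sample size rests on serum supply, and no AE rate is stated. The check sets the rules side by side, then bounds the effect.

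**1. Trace one event.** Take injection-site pain with onset on Day 3 that resolves on Day 12 (invented dates).

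| Step | Rule | Result |
|---|---|---|
| Solicited tables, Days 1 to 7 | SAP 10.1.3.1 | Counted |
| Entry on the AE eCRF | Protocol 10.1.2, 10.4.2; SAP 10.1.3 | Yes in both; the SAP adds the label unsolicited |
| Filter: recorded after the dose | SAP 10.1.4 | Passes |
| 28-day unsolicited row | SAP 10.1.4.1 | Counted |
| Onset interval | SAP 10.1.4 | Day 1 to 7 if Day 3 is entered; Day 8 to 28 if Day 8 is entered. The SAP does not say which |
| Related row | SAP 10.1.4.1 | Depends on the causality entered (protocol 10.4.1) |

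**2. Look for a rule that removes it.** SAP 10.1 counts a subject once per SOC and PT, but only within a summary, so it does not prevent overlap between the solicited and unsolicited tables. Protocol 9.3.3 sends newly reported unsolicited events to the same AE eCRF, so the page alone does not separate the two kinds. Protocol 10.4.1 lists the items documented per event, and a solicited or persistent identifier is not among them; the eCRF itself is not in the documents and may have one.

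**3. Bound the effect on the 28-day unsolicited row.** Inputs: N = 80 (protocol 13.3, SAP 6), assuming all are dosed; k affected subjects (assumed).

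- Per subject: 1/80 = 1.25 percentage points if the subject has no other unsolicited AE in the row, and 0 otherwise.
- For k subjects: between 0 and 1.25 × k points.

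| k (assumed) | Increase, percentage points |
|---|---|
| 1 | 0 to 1.25 |
| 2 | 0 to 2.5 |
| 4 | 0 to 5 |
| 8 | 0 to 10 |

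For example, four subjects with no other unsolicited AE would move an assumed 16/80 = 20% to 20/80 = 25%.

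**4. Would the rule be used at all?** If a proportion p of subjects has a persistent reaction, the chance of at least one is 1 − (1 − p)^80. For assumed p of 1%, 2%, 5% and 10% this is 55%, 80%, 98% and above 99.9%.

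**5. Duration (separate, minor).** Protocol 13.1.4 reports the number of days with the event; SAP 10.1.3 reports the longest unbroken run; SAP 10.1.3.1 says only duration in days. Symptoms on Days 1, 2, 5 and 6 give 4 days by the first measure and 2 by the second. Onset on Day 5 with an AE eCRF end date of Day 12 gives 3 diary days (5, 6, 7), but 12 − 5 + 1 = 8 days to the end date.

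**The case against.** The best defence is that the SAP sentence concerns data capture and that both documents send the event to the same page. The protocol only makes a separate analysis possible; 13.1.4 schedules none. Since the solicited endpoints stop at 7 days, calling the continuation unsolicited gives it a place in the tables. The tables are descriptive, and listings allow any overlap to be traced.

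Much of this stands and limits the point. It does not remove it: the SAP label has no rule to reverse it, the departure is undeclared, and listings do not correct a reported percentage.

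Several stronger readings are tempting but unsupported:

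- *The SAP omits an analysis that the protocol requires.* The protocol permits one and does not require it.
- *The CSR sentence in protocol 10.4.2 settles how the continuation is classed.* It refers to the 7-day diary events, which the SAP does tabulate as solicited.
- *Persistent local reactions must inflate the related row.* Protocol 10.2 treats solicited local AEs as related by default, but 10.4.1 asks for the investigator's causality opinion on each event, and it is unclear which applies once the event is relabelled.
- *The Day 1 to 7 unsolicited row is inflated.* That depends on the onset date entered.
- *A rise of up to 10 points is to be expected.* That is only the upper bound for an assumed eight subjects.

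On duration, protocol 13.1 leaves variable definitions to the SAP, so the different measure is a refinement to declare and adds little weight here.

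**Conclusion.** The conflict is real and should be fixed, with limited stakes. SAP 10.1.3 gives prolonged solicited reactions a label that conflicts with protocol 10.1.2 and 10.4.2, and SAP 10.1.4 and 10.1.4.1 exclude nothing. On a literal reading, one event is therefore counted under a solicited and the unsolicited secondary endpoint.

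Confidence is high on the wording conflict and the missing exclusion. The numerical effect is conditional: 0 to 1.25 points per affected subject in the 28-day row, assuming that 80 are dosed, that persistent reactions occur, and that the SAP is programmed as written. No test, sample size or primary endpoint is affected.

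**What to change.** Replace the SAP 10.1.3 sentence with text such as:

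> Solicited reactions with onset in Days 1 to 7 that are entered on the AE eCRF (because they continue on Day 8, lead to withdrawal, or are serious) are flagged as solicited in the analysis dataset. They are excluded from the unsolicited AE tables and onset intervals in 10.1.4 and 10.1.4.1. They remain in the AE overview, in the SAE and withdrawal tables as applicable, and in the listings. Those continuing on Day 8 are listed or summarised separately with the AE eCRF end date.

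Covering withdrawal and seriousness matters because protocol 10.4.2 sends those events to the same page even if they resolve by Day 7.

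Use an eCRF identifier if one exists. Otherwise flag only events whose AE eCRF onset falls in Days 1 to 7 and matches the diary event, with manual review before database lock. Matching on term alone could remove a genuinely new headache or diarrhea that starts on or after Day 8; such events must stay unsolicited.

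If the sponsor does intend the SAP convention, the lesser remedy is to declare it in SAP 13 and footnote the unsolicited tables. That makes the overlap visible but leaves it in the counts.

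For duration, use the protocol 13.1.4 measure for the diary period or declare the change in SAP 13, and label time to the AE eCRF end date as a separate measure.

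Cost: SAP wording, one derived flag, one exclusion and one small listing or table, plus the manual review if no identifier exists. No new subject data are needed.

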##### **10.1.3.1 Summaries**

The summaries for solicited AEs will be:

- The number and percentage of subjects with solicited local and systemic reactions during the first 7 days (including day of administration) after the trial vaccine dose by day and overall.
- The number and percentage of subjects with solicited local and systemic reactions during the first 7 days (including day of administration) after the trial vaccine dose by severity, day and overall.
- The number and percentage of subjects with solicited local and systemic reactions during the first 30 minutes after the trial vaccine dose.

- The number and percentage of subjects with solicited local and systemic reactions during the first 30 minutes after the trial vaccine dose by severity.
- Summary of the day of first onset of each solicited AE.
- Summary of the duration (days) of each solicited AE.

A horizontal stacked bar plot showing the percentage of participants with each solicited AE after the trial vaccine dose. This plot will break down the percentages by maximum severity, with the percentage of mild, moderate and severe events stacked for each solicited AE.

All solicited AEs will also be listed.

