- Starting on the day of trial vaccine administration, the subject will check for specific types of events at the injection site, any specific generalized symptoms (solicited systemic AEs), body temperature (any method), any other symptoms or change in the subject's health status, and any medications taken (excluding vitamins and minerals). These solicited AEs, body temperature, other symptoms and medications will be recorded in the diary card. Assessments should preferably take place in the evening.
- Temperature measurement is to be performed using the thermometer provided by the site. If the subject feels unusually hot or cold during the day, the subject should check their temperature. If the subject has fever, the highest body temperature observed that day should be recorded in the diary card.
- The measurements of solicited local AEs are to be performed using the ruler provided by the site.
- The collection in the diary card of body temperature, solicited local AEs, and solicited systemic AEs will continue for a total of 7 days after trial vaccine administration (Day 1).
- The use of analgesic/antipyretic medications to treat symptoms associated with trial vaccine administration will be recorded in the diary card during the reporting period (Day 1 to Day 7).

After trial vaccine administration, the subject will be observed for at least 30 minutes including observation for unsolicited AEs, solicited local AEs, solicited systemic AEs, and body temperature measurement. Information should be recorded in the eCRF. The investigator or delegate will take the opportunity to remind the subject how to measure solicited local AEs and body temperature as part of this observation period. All safety data will be collected in the subject's source documents.

The site staff should schedule the next trial activity reminder call or site visit.

CONFIDENTIAL

The subject will receive a written reminder of the next planned trial activity. The subject will be reminded to complete the diary card daily and to contact the site if there are any questions and to contact the site immediately (or as soon as the subject is medically stable) if the subject has a medical condition that leads to a hospitalization or an emergency room visit. All contact details will be provided to the subject.

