13.1.4 Secondary Analysis - Safety

Safety data will be summarized by computing number and percentage of subjects who experienced an AE.

Solicited AEs

Solicited AEs will be assessed 30 minutes after administration of trial vaccine then daily for 7 days (including the day of administration). Summaries will be provided for each solicited AE, daily from Day 1 to Day 7 after administration of trial vaccine (including the day of dose) and overall. Solicited local AEs and systemic AEs will also be summarized by severity. For subjects

CONFIDENTIAL

with more than 1 episode of the same event within the Day 1 to Day 7 period, the maximum severity will be used for overall tabulations. Body temperature measurements will be summarized in categories (including fever, defined as temperature $\geq 38^{\circ}\text{C}$). Summaries of the day of first onset of each event and the number of days subjects experienced each event will also be provided. Data from the 30-minutes assessment will be summarized separately.

Unsolicited AEs

Unsolicited AEs, SAEs, and AEs leading to withdrawal from the trial will be coded using the MedDRA and summarized by preferred term (PT) and system organ class (SOC). Subjects reporting more than 1 occurrence for the term (level) being summarized will be counted only once for this term. Unsolicited AEs collected up to 28 days after administration (including the day of administration) of trial vaccine, will be summarized by severity (mild, moderate, severe) and relationship (not related, related) to trial vaccine or trial procedures. If a subject reported more than one AE within an SOC or PT then the event with the maximum severity and strongest relationship (causality) to trial vaccine or trial procedure will be included in the summaries. Any unsolicited AE will be summarized using the day of onset for the following 3 time intervals: 1) Day 1 to Day 28, 2) Day 1 to Day 7, and 3) Day 8 to Day 28.

SAEs and AEs leading to withdrawal from the trial will be summarized for Day 1 to Day 28, and overall (up to Day 85).

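### The SAP does not define solicited-AE duration or say whether the AE eCRF end date is used; if only diary days are counted, reactions continuing on Day 8 are right-censored and reported as 7 days at most

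*SAP*

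**What the plan says.** **Collection window.** Protocol 9.3.3: "The collection in the diary card of body temperature, solicited local AEs, and solicited systemic AEs will continue for a total of 7 days". SAP 10.1.3 has solicited reactions assessed at 30 minutes "and then daily for 7 days (including the day of administration").

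**Reactions that continue.** Protocol 10.1.2 moves a solicited AE still present on Day 8 to the AE eCRF: "For these persistent/prolonged solicited AEs the end date will be captured on the AE eCRF". Protocol 10.4.2 repeats the rule and gives its purpose: "the end date will be captured on the AE eCRF to permit a separate analysis from the unsolicited AEs". SAP 10.1.3 treats the same reactions differently: "Any solicited local or systemic reactions observed as continuing beyond 7 days following the trial vaccine dose will be recorded as an unsolicited AE".

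**Duration.** Three descriptions are in force:
- Protocol 13.1.4: "the number of days subjects experienced each event will also be provided".
- SAP 10.1.3: "the maximum number of continuous days subjects experienced each event will also be provided".
- SAP 10.1.3.1: "Summary of the duration (days) of each solicited AE".

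None of the three names a data source or says what happens when a reaction outlasts the diary.

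**The concern.** The protocol collects an end date for the reactions that outlast the diary, and collects it for a stated analysis. The SAP neither plans that analysis nor says that the date enters the duration summary. Its solicited assessments end at Day 7, and whatever continues is reclassified as unsolicited. A programmer working from SAP 10.1.3 and 10.1.3.1 would most naturally count diary days.

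A reaction still present when the diary closes is then right-censored but summarised as if complete. Its remaining days are left out, and the largest reported duration can only be 7. These are the reactions that say most about tolerability, and safety is the trial's only secondary objective. As unsolicited AEs, they may also enter the unsolicited tables of SAP 10.1.4.1, the mixing that the protocol's separate analysis was meant to avoid.

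The protocol's day count and the SAP's longest continuous run also differ for an intermittent reaction. Two analysts could therefore produce different duration tables from the same data.

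**Working it through.** The plan states no figure for solicited-AE duration, so there is nothing to reproduce. The check has three parts.

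**1. Day counting (certain if only diary days are counted).** Day 1 is the day of vaccination, and the diary covers Days 1 to 7 (Protocol 9.3.3).

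- Diary-only duration = min(end day, 7) − onset day + 1.
- Duration with the AE eCRF end date = end day − onset day + 1.
- Days lost = max(0, end day − 7).

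| Onset | End | With eCRF end date | Diary only | Lost |
|---|---|---|---|---|
| Day 1 | Day 7 | 7 | 7 | 0 |
| Day 1 | Day 10 | 10 | 7 | 3 |
| Day 2 | Day 12 | 11 | 6 | 5 |
| Day 2 | Day 14 | 13 | 6 | 7 |
| Day 6 | Day 12 | 7 | 2 | 5 |

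The diary-only maximum is 8 − onset day: 7 for onset on Day 1, 6 for Day 2, down to 1 for Day 7. Reactions that end by Day 7 are unaffected.

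**2. Effect on the mean (all inputs assumed).** The documents give no durations or persistence rates. Take onset as equally likely on Days 1, 2 and 3, and duration as geometric with mean m. Let q = 1 − 1/m.

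- A reaction with onset on day s persists past Day 7 with probability q^(8 − s), so the share persisting is P = (q^7 + q^6 + q^5)/3.
- For a geometric duration cut at L days, the mean is m(1 − q^L), so the reported mean is m(1 − P).
- Among persisting reactions, the reported mean is (7q^7 + 6q^6 + 5q^5)/(q^7 + q^6 + q^5). The true mean is that value plus m, because the geometric distribution has no memory.

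| Assumed m | Share persisting P | Reported mean m(1 − P) | Persisting reactions: true mean, reported mean |
|---|---|---|---|
| 2 | (0.0078 + 0.0156 + 0.0313)/3 = 1.8% | 1.96 | 7.6, 5.6 |
| 3 | (0.0585 + 0.0878 + 0.1317)/3 = 9.3% | 2.72 | 8.7, 5.7 |
| 4 | (0.1335 + 0.1780 + 0.2373)/3 = 18.3% | 3.27 | 9.8, 5.8 |

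The overall mean hardly moves at m = 2. The values for persisting reactions are understated by m days on average in every row.

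**3. Chance that it arises at all.** With 80 subjects and an assumed per-subject rate p of a persisting reaction, the chance of at least one is 1 − (1 − p)^80. This gives 33% for p = 0.5%, 55% for 1%, 80% for 2% and 98% for 5%.

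**The case against.** **No document caps duration at Day 7.** A reader might infer that the SAP prescribes a diary-only duration that can never exceed 7 days. It does not. The count summaries in SAP 10.1.3.1 are limited in words to the first 7 days or the first 30 minutes, but the duration item is not. Protocol 10.4.1 documents start date, end date and duration for each event on the AE eCRF. SAP 7.3.1 imputes partial AE dates in order to calculate duration. An analyst could therefore use the eCRF end date under the present text. This stands, and it is why the point is conditional. It does not close the gap, because none of these sections connects those dates to the solicited summary.

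**Days within the window may be the intended quantity.** The endpoint is solicited AEs up to 7 days after the dose, and a count of days with a reaction in Days 1 to 7 is a legitimate description, unbiased for what it measures. That is fair, and a label saying so would remove the ambiguity in the duration table. It would still leave out the protocol's separate analysis of persisting reactions.

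**Persisting reactions are not lost.** They are on the AE eCRF and will appear in the AE listings. In an open-label trial of 80 subjects with no comparator, each case stays individually visible. This stands, and it limits the consequence to how duration is summarised and classified.

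**The size is assumed.** This also stands. The uniform onset and the memoryless tail have no basis in the documents, and the m = 2 row shows a trivial change in the mean.

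**Conclusion.** The point holds as a gap between protocol and SAP. Duration is undefined, it is described in three ways, and the SAP's reclassification of continuing reactions as unsolicited omits an analysis for which the protocol collects the end date. Understated durations follow only if the summary counts diary days alone, which is the natural reading but not a written rule.

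On that reading, each reaction continuing on Day 8 loses its end day minus 7 days, and the reported maximum is 7 at most. The effect on the mean is unknown. Under the assumptions above it runs from 2.00 reported as 1.96 to 4.00 reported as 3.27, and it is negligible if persistence is rare. A claim that duration will be materially biased in this trial would go beyond the documents.

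The importance is modest. This is one descriptive secondary safety summary. The primary immunogenicity analysis and the solicited incidence and severity tables are unaffected.

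**What to change.** Amend SAP 10.1.3 and 10.1.3.1 as follows.

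1. Choose one definition of duration, either days with the event or longest continuous run. Use it in both SAP sections and reconcile it with Protocol 13.1.4.
2. Add a derivation rule, for example:

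> For a solicited AE continuing on Day 8, duration runs from the first diary day of that continuous episode to the end date on the AE eCRF. An event with no end date is reported as ongoing (censored), is counted in a separate row and is not dropped.

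3. State how ongoing events enter the statistics. A median and range with censored values marked would do; a mean over completed events alone would again leave out the longest.
4. Flag durations that rest on an imputed end date. SAP 7.3.1 sets a month-only stop date to the last day of the month, which can overstate duration.
5. Add the number and percentage of subjects whose reaction continued beyond Day 7, by solicited AE.
6. Flag these events as persistent solicited AEs and summarise them separately from unsolicited AEs, as Protocol 10.1.2 and 10.4.2 foresee.

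The cost is one derivation linking two existing eCRF pages and a few table rows. No new data are needed. Where reactions persist, reported durations become slightly longer.
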